Section 6.7	This section clarifies that subject may use up to 16 sprays per application, however this will depend on the number of lesions.
Section 8.2.2	Wording around timing of Washout period is being added for further clarification.
Section 9.3.5	This section of the protocol is being clarified that, as per the Schedule of Activities (Section 1.3), the first investigational product application will happen in the study center under clinical staff supervision, after the completion of the baseline assessments. All subsequent study application will be administered by the parent/guardian or by the subject in the setting of subject’s home.
Section 9.4.2	There was a typo in this section of the protocol and it is being clarified that, as per Inclusion Criteria (Section 5.1) Number 8: Female subjects aged ≥11 years old, or female patients <11 years old who have started menstruating, will have urinary pregnancy test performed at all visits. The Baseline result must be available and must be negative before the subject apply the first application of IP. Positive pregnancy test will

	disqualify the subject from the participation in the study.
Section 9.4.4	This section of the protocol is being clarified that, as per the Schedule of Activities (Section 1.3), Body weight and height will be measured at Screening and at Day 28/Final Visit (or at Early Termination Visit, as applicable).
Appendix 5	This section of the protocol is being clarified that, as per Inclusion Criteria (Section 5.1) Number 8, females must either practice abstinence from heterosexual contact or use one (1) of the highly effective contraceptive options described in the Appendix 5. Females are not required to use two (2) highly effective methods of contraception

Administrative changes: Minor changes involving grammar, wordsmithing, punctuation, and other editorial changes have been made throughout the document. All are clearly identified in the track-changes version of the amendment.

Additional formatting and stylistic adjustments have been made to facilitate the reading process.

TABLE OF CONTENTS

1.0	PROTOCOL SUMMARY	9
1.1	Synopsis	9
1.2	Schema.....	11
1.3	Schedule of Activities	12
2.0	INTRODUCTION.....	15
2.1	Study Rationale	15
2.2	Background	15
2.3	Benefit/Risk Assessment	16
3.0	OBJECTIVES AND ENDPOINTS	18
4.0	STUDY DESIGN.....	19
4.1	Overall Design	19
4.2	Scientific Rationale for Study Design	20
4.3	Justification for Dose	20
4.4	End of Study Definition	20

1.0 PROTOCOL SUMMARY

1.1 Synopsis

Protocol Title: An open-label, multicenter, Phase Ib study of B244 delivered as a topical spray to assess safety in pediatric subjects aged 2 to 17 years with atopic dermatitis

Rationale:

Clinical studies with topical administration of B244 have been conducted in subjects with acne, hypertension, atopic dermatitis, and rosacea. There have been no safety signals observed to date.

The aim of this study is to assess the safety of B244 in pediatric subjects aged 2 to 17 years with atopic dermatitis.

Objectives and Endpoints

Objectives	Endpoints
Primary	
 Assessment of the safety and tolerability of B244 in pediatric subjects with atopic dermatitis.
Exploratory	
 Incidence of treatment-emergent adverse events (TEAEs). Change from Baseline in physical examination at each post baseline visit. Change from Baseline in vital signs at each post baseline visit. 
 Efficacy of B244 on signs and symptoms of atopic dermatitis. Efficacy of B244 on patient oriented measure of atopic dermatitis. Efficacy of B244 on patient reported assessment of atopic dermatitis. 
 Changes from Baseline to post baseline visits in: 
 Validated Investigator Global Assessment for Atopic Dermatitis (vIGA-AD) scale. Area Severity Index (EASI) score and each component of EASI from Baseline to post baseline visits. Changes in Patient Oriented Eczema Measure (POEM total score and each of the 7 components) from Baseline to post baseline visits. Changes in patient reported outcome (self-reported ItchMan questionnaire) from Baseline to post baseline visits.

Overall Design:

This is a Phase 1b, open-label, multiple site study assessing twice daily B244 application for 28 days in pediatric subjects with atopic dermatitis.

The study will enroll 36 subjects in 3 cohorts of 12 subjects:

- Cohort 1: subjects aged 2 to 5 years.
- Cohort 2: subjects aged 6 to 11 years.
- Cohort 3: subjects aged 12 to 17 years.

Number of Investigators and Study Centers:

Approximately 6 Investigators and study centers are expected to participate in this study.

Number of Subjects:

The study will enroll 36 subjects in 3 cohorts of 12 subjects:

- Cohort 1: subjects aged 2 to 5 years.
- Cohort 2: subjects aged 6 to 11 years.
- Cohort 3, subjects aged 12 to 17 years.

Treatment Groups and Duration:

Subjects will attend for a Screening visit between Days -21 and -14. If all eligibility criteria and none of the exclusion criteria are met, subjects will be enrolled into the study and will be required to undergo a 14 day washout period (Days-14 to -1). Subjects will attend the study center on Day 1(-1 to 1) and the Baseline assessments will be performed before application of the first dose. On confirmation of continued eligibility the subject and parent or guardian of the subject will be coached on how to apply medication, depending on the affected areas. They will be instructed to apply B244 twice daily (approximately 12 hours apart) for 28 days. The first dose will be applied in the clinic under the supervision of clinical staff. Details of dose administration will be recorded in the study diary provided.

The subjects with their parent or guardian will return to the study center on Days 7, 14, and 21 for completion of study assessments. There will be a final study visit on Day 28, this will be defined as the end of the study for the subjects. A time window of ± 2 day will be permitted for these 4 visits. There will not be a period of confinement in the study center all visits will be outpatient visits.

Safety monitoring will include review of TEAEs, vital signs and physical examination.

Efficacy will be assessed using EASI, vIGA-AD scale, POEM and ItchMan scores.

Statistical Methods:

All subjects who are enrolled and take at least 1 dose of study treatment will be included in the Intent to Treat (ITT) population. The ITT population will be the primary population for safety and efficacy assessments.

[figure not shown]
All subjects in the ITT population without any protocol deviations that may have an impact on the efficacy assessments will be included in the Per Protocol (PP) population. The PP population will be the supportive population for efficacy assessments.

The sample size is not based on statistical considerations but is typical for studies of this nature, and is considered adequate to characterize the distribution of the planned endpoints. Any statistical testing will be considered exploratory and descriptive.

Data Monitoring Committee: No

1.2 Schema

Figure 1 Study Schema

1.3 Schedule of Activities

Table 1.1 Schedule of Assessments

Visit Name	Screening	Washout	Baseline (Day 1)	Day 7	Day 14	Day 21	Day 28 Final Visit	Early Termination Visit
Study Center Visit	1		2	3	4	5	6	
Visit Window in Days	-21 to -14	-14 to -1	-1 to 1	±2	±2	±2	±2	
Informed Consent	X							
Inclusion/Exclusion Criteria	X		X					
Demographics	X							
Medical History	X							
Hanifin and Rajka Criteria	X		X					
Physical Examination	X		X	X	X	X	X	X
Urine Pregnancy Test ¹	X		X				X	X
Body Weight	X						X	X
Height	X						X	X
Vital Signs ²	X		X	X	X	X	X	X
Validated Investigator Global Assessment for Atopic Dermatitis (vIGA-AD) Scale	X		X	X	X	X	X	X
Eczema Area Severity Index (EASI)	X		X	X	X	X	X	X
Patient Oriented Measure (POEM) ³	X		X	X	X	X	X	X
ItchMan Questionnaire	X		X	X	X	X	X	X
Dispense Investigational Product to Subject ⁴			X	X	X	X		

Visit Name	Screening	Washout	Baseline (Day 1)	Day 7	Day 14	Day 21	Day 28 Final Visit	Early Termination Visit
Study Center Visit	1		2	3	4	5	6	
Visit Window in Days	-21 to -14	-14 to -1	-1 to 1	±2	±2	±2	±2	
Investigational Product Application ⁵			X	X	X	X	X	
Collect Investigational Product from Subject ⁶				X	X	X	X	
Investigational Product Compliance ⁶				X	X	X	X	X
Counseling ⁷			X	X	X	X		
Study Cleanser ⁸	X	X	X	X	X	X	X	X
Moisturizer ⁸	X	X	X	X	X	X	X	X
Study Diary ⁹			X	X	X	X	X	X
Adverse Events Recording ¹⁰	X	X	X	X	X	X	X	X
Concomitant Medications	X		X	X	X	X	X	X

1. Urine pregnancy test will be administered to females 11 years of age or older.
2. Pulse rate, temperature and blood pressure will be obtained. Subject should be allowed to rest for >5 minutes sitting, then a single blood pressure and pulse rate measurement will be performed, using the non-dominant arm with a calibrated electronic sphygmomanometer.
3. Patient Oriented Measure questionnaire is to be filled out by the subject or the parent or guardian.
4. At Baseline, depending on the age of the participant, 1 or 2 bottles will be supplied. Total number of bottles to be dispensed to the subjects for the duration of the study will depend upon the body surface area affected by atopic dermatitis (Section 6.1). At each visit, study staff will determine each subject's usage and supply additional investigational product if necessary.
5. The first investigational product application will happen in the study center under clinical staff supervision after completion of the baseline assessments. Subjects and parent or guardian will be coached on how to apply the study treatment depending on the affected area and will be asked to apply the study treatment twice daily.
6. Weight of an investigational product kit will be obtained at the at the Baseline visit. Study staff will be asked to weigh dispensed bottles PRE FIRST DOSE. Weight will be recorded in grams. Subjects will be asked to bring their bottles back for every visit. Upon return for the study visit, bottles will be weighed again.

7. Subjects will be counseled on the use of the study treatment, study diary and any questions the subject, parent or guardian may have will be answered.
8. The Sponsor will provide a biome friendly, preservative-free moisturizer and cleanser to be used as needed, at the discretion of the parent or guardian. Any remaining moisturizer or cleanser will be returned to the Investigator at the Final Visit (Day 28) or the Early Termination Visit.
9. The subject, parent or guardian will be asked to fill out a daily study diary.
10. Adverse events will be monitored throughout the trial, starting with the time informed consent form has been signed.

2.0 INTRODUCTION

2.1 Study Rationale

AOBiome Therapeutics has isolated a purified strain of *Nitrosomonas eutropha*, designated *Nitrosomonas eutropha* D23, from soil samples. Sequencing of the *Nitrosomonas eutropha* D23 genome revealed a distinct genetic profile from that of other published *Nitrosomonas* strains and ammonia (NH₃) oxidizing bacteria (AOB) genomes. The unique metabolic and antimicrobial activity of *Nitrosomonas*, in combination with their complete lack of virulence, render these bacteria as attractive candidates for topical delivery of nitrite (NO₂) and nitric oxide (NO) on human skin. This has potential to improve health in both normal and abnormal skin conditions (including wound sites). The drug product has been designated the code B244.

Clinical studies with topical administration of B244 have been conducted in subjects with acne. In addition, other clinical studies, either ongoing or completed, have included the investigation of the efficacy of B244 in subjects with hypertension, atopic dermatitis, and rosacea. The results of these studies have indicated efficacy of B244 with no unexpected safety signals. The aim of this study is to assess the safety of B244 in pediatric subjects aged 2 to 17 years with atopic dermatitis.

2.2 Background

Ammonia oxidizing bacteria are ubiquitous in the environment and are essential for the initial step in nitrification processes, specifically the oxidation of NH₃ to NO. They are found in all soils and water sources (fresh, ground, and seawater). *Nitrosomonas*, as AOBs, are gram-negative chemolithoautotrophic betaproteobacteria that obtain energy solely from NH₃ oxidation, while fixing carbon dioxide (CO₂) for their carbon needs [[Arp and Sayavedro-Soto, 2001](#)].

It is hypothesized that there may be regulation of basal NO levels by AOB on the skin. In acne, for example, *Nitrosomonas eutropha* might be expected to down regulate androgen levels. Low NO causes high androgen levels. Increasing NO/NO₂ by the oxidation of NH₃ in sweat by *Nitrosomonas eutropha* may decrease androgen levels. Androgens, the male hormones present in men and women, can contribute to acne flares by over stimulating the oil glands and altering the development of skin cells that line hair follicles in the skin. Increasing NO/NO₂ production may therefore have a critical role in controlling the signs and symptoms of acne vulgaris. In this regard, the disruption of the normal AOB component of the human microbiome has the potential to disrupt the feedback regulation between acne, NO, and androgens. Nitrogen oxide releasing drugs or NO donors have also shown activity against *Propionibacterium acnes* and other pathogenic bacteria, anti-inflammatory activity, and inhibition of lipogenesis by insulin-stimulated immortal sebocytes ([Weller and Price, 2001](#), [Rico et al, 2014](#)).

Other important potential mechanisms through which *Nitrosomonas eutropha* D23 could positively effect acne and other skin diseases include an anti-inflammatory and antimicrobial effects

Clinical studies with topical application of B244 have been conducted, or are planned, include studies in subjects with clinical diagnosis of facial acne vulgaris (Investigational New Drug [IND] 16487) hypertension (IND 17086), atopic dermatitis (IND 17485) and mild to moderate rosacea (IND 18086). Overall, there have been no serious adverse events (SAE) or unexpected safety signals observed following treatment with B244.

Efficacy was supported by statistically significant 2-point reduction in Investigator Global Assessment (IGA) with B244 and a trend in the reduction of the number of inflammatory lesions compared with vehicle in the study conducted in subjects with facial acne vulgaris (IND16487).

B244 is comprised of *Nitrosomonas eutropha* D23 diluted in storage solution (50 mM Na₂HPO₄ and 2 mM MgCl₂, pH 7.6 ± 0.2). The B244 drug product is provided as a mist formulation in sterilized 7.5 or 30 mL plastic containers with appropriate sized and intended use designed spray nozzles. There are 3 concentrations, measured by optical density (OD), of the drug product: high dose (OD₆₀₀ 4.0 ± 0.8 equivalent to 8 × 10⁹ cells/mL), middle dose (OD₆₀₀ 2.0 ± 0.4 equivalent to 4 × 10⁹ cells/mL), and low dose (OD₆₀₀ 1.0 ± 0.2 equivalent to 2 × 10⁹ cells/mL).

A detailed description of the chemistry, pharmacology, efficacy, and safety of B244 is provided in the current [Investigator's Brochure](#).

2.3 Benefit/Risk Assessment

To date, there have been no reported infections or health risks associated with topical application or ingestion of *Nitrosomonas* species. The absence of any known illnesses attributed to these bacteria despite widespread human exposure suggests that they are unlikely to pose significant health risk. Infection or tissue damage by *Nitrosomonas* is unlikely, because the sequenced genomes of several *Nitrosomonas* and other AOB lack genes encoding cytotoxins, or other known bacterial virulence factors. Further, AOB are slow growing, as compared to most heterotrophic bacteria, with optimum doubling times of 8 hours or higher. In particular, *Nitrosomonas* growth is rate limited by the availability of ammonia requiring the oxidation of 27 moles NH₃/mole CO₂ fixed. Due to their dependence on ammonia for their growth, the numbers of *Nitrosomonas* on the skin will be necessarily limited and naturally regulated by the amount of ammonia produced in sweat. This would ensure that the amount of nitrite and NO generated would be relatively low, mitigating the risk of adverse effects due to high NO/NO₂ low without any adverse effects.

The Sponsor will immediately notify the Principal Investigator if any additional safety or toxicology information becomes available during the study.

This study will be performed in compliance with the protocol, International Council on Harmonisation of Technical Requirements for Registration of Pharmaceuticals for Human Use (ICH) Good Clinical Practice (GCP) and applicable regulatory requirements. Aspects of the study concerned with the investigational product (IP) will meet the requirements of Good Manufacturing Practice (GMP).

3.0 OBJECTIVES AND ENDPOINTS

Table 3.1 Study Objectives and Endpoints

Objectives	Endpoints
Primary	
 Assessment of the safety and tolerability of B244 in pediatric subjects with atopic dermatitis.
Exploratory	
 Incidence of treatment-emergent adverse events (TEAEs). Change from Baseline in physical examination at each post baseline visit. Change from Baseline in vital signs at each post baseline visit. 
 Efficacy of B244 on signs and symptoms of atopic dermatitis. 
 Changes from Baseline to post baseline visits in: 
 Validated Investigator Global Assessment for Atopic Dermatitis (vIGA-AD) scale. Area Severity Index (EASI) score and each component of EASI from Baseline to post baseline visits. Changes in Patient Oriented Eczema Measure (POEM total score and each of the 7 components) from Baseline to post baseline visits. Changes in patient reported outcome (self-reported ItchMan questionnaire) from Baseline to post baseline visits.

4.0 STUDY DESIGN

4.1 Overall Design

This is a Phase 1b, open-label, multiple site study assessing twice daily B244 application for 28 days in pediatric subjects with atopic dermatitis.

The study will enroll 36 subjects in 3 cohorts of 12 subjects:

- Cohort 1: subjects aged 2 to 5 years.
- Cohort 2: subjects aged 6 to 11 years.
- Cohort 3: subjects aged 12 to 17 years.

At Screening and Baseline, all subjects must have confirmed diagnosis of atopic dermatitis, as defined by the Hanifin and Rajka criteria, which involves a minimum of 10% but no more than 60% body surface area and a Validated Investigator Global Assessment for Atopic Dermatitis (vIGA-AD) scale of 2 or 3.

Subjects will attend for a Screening visit between Day -21 and -14. If all eligibility criteria and none of the exclusion criteria are met, subjects will be enrolled into the study and will be required to undergo a 14 day washout period (Day-14 to -1). The washout period is to ensure the subjects do not have any active systemic infections (including but not limited to, ear infections, upper respiratory tract infections, throat infections) and that they comply with the withdrawal of medications included in [Exclusion Criterion 7](#). On completion of the washout period and confirmation of continued eligibility the subjects will be assigned to one of the cohorts based on the age of the subject.

Subjects will attend the study center on Day 1 (-1 to 1) and the Baseline assessments listed in [Table 1.1](#) will be conducted. On confirmation of continued eligibility, the subject and parent or guardian of the subject will be coached on how to apply medication, depending on the affected areas. They will be instructed to apply B244 twice daily (approximately 12 hours apart) for 28 days and record the details of the application in the study diary provided. They will also be provided guidance on the storage of the study treatment. Guidance for the application of B244 is provided in [Section 6.1](#). The first dose will be administered on Day 1 in the clinic, under the supervision of clinical staff, subsequent doses can be applied outside of the clinic. The importance of adherence to the medication schedule will be reinforced at each study visit.

The subjects with their parent or guardian will return to the study center on Days 7, 14 and 21 when the assessments listed in [Table 1.1](#) will be conducted. There will be a final study visit on Day 28, this will be defined as the end of the study for the subjects. A time window of ± 2 day will be permitted for these visits.

Safety monitoring will include review of TEAEs, vital signs and physical examinations as indicated in [Table 1.1](#).

Efficacy will be assessed using EASI, vIGA-AD scale, POEM, and ItchMan scores Table 1.1.

4.2 Scientific Rationale for Study Design

AOBiome Therapeutics has developed B244 as a topical application of a natural source of AOB and NO/NO₂ to the human skin. B244 for topical delivery has the potential to improve health in both normal and abnormal skin conditions or wound sites.

A standard parallel-group, open-label design is used for this study to evaluate the safety and tolerability of B244 in pediatric subjects with atopic dermatitis.

The study will be conducted in pediatric subjects with atopic dermatitis because they are a target population.

The sample size for each cohort is based on the desire to obtain adequate safety and tolerability data to achieve the objectives of the study while exposing as few subjects as possible to B244 and study procedures.

This study will be performed in compliance with the protocol, the ICH GCP, GMP, and applicable regulatory requirements.

4.3 Justification for Dose

There are 3 concentrations of the drug product available: high dose (OD₆₀₀ 4.0 ± 0.8 equivalent to 8 × 10⁹ cells/mL), middle dose (OD₆₀₀ 2.0 ± 0.4 equivalent to 4 × 10⁹ cells/mL) and low dose (OD₆₀₀ 1.0 ± 0.2 equivalent to 2 × 10⁹ cells/mL).

The middle dose has been selected for this study to minimize the exposure while ensuring administration of a dose considered likely to show improvement in symptoms of atopic dermatitis.

4.4 End of Study Definition

The end of the study is defined as the date of last scheduled procedure shown in the Table 1.1 for the last subject in the study.

4.5 Dose Escalation Criteria

There will not be any dose escalation in this study.

4.6 Study Stopping Criteria

Dosing for any individual subject will be stopped if:

- The subject experiences a possibly drug-related SAE.
- The subject experiences a possibly drug-related significant non-serious adverse event (AE), which in the opinion of the Principal Investigator, Chief Investigator, Medical Monitor, or

Sponsor's medical representative, warrants discontinuation from the study for that subject's wellbeing. The occurrence of significant non-serious AEs as described above will require that further dosing of other subjects be evaluated by the Chief Investigator, the Medical Monitor and the Sponsor's Medical Advisor to determine study discontinuation.

- The subject's atopic dermatitis worsens and requires alternative or supplemental medication during the study (see [Section 6.8](#) for allowed treatments).
- The subject or his/her parent or guardian choose to discontinue for any reason.

Dosing for a cohort will be stopped if:

- A subject experiences a possibly drug-related SAE.
- More than 2 subjects experiences a possibly drug-related significant non-serious AE, which in the opinion of the Principal Investigator, Chief Investigator, Medical Monitor, or Sponsor's medical representative, warrants discontinuation from the study for that subject's wellbeing. The occurrence of significant non-serious AEs as described above will require that further dosing of other subjects be evaluated by the Chief Investigator, the Medical Monitor and the Sponsor's Medical Advisor to determine study discontinuation.

The study will be stopped if:

- More than 1 subject experiences a drug-related SAE.

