7.0 DISCONTINUATION OF STUDY TREATMENT AND SUBJECT DISCONTINUATION/WITHDRAWAL

7.1 Discontinuation of Study Treatment

The stopping criteria for the study are described in Section [4.6](#).

If a subject who does not meet enrollment criteria is inadvertently enrolled, that subject must be discontinued from study treatment and the Sponsor or Sponsor designee must be contacted. An exception may be granted in rare circumstances for which there is a compelling safety reason to allow the subject to continue. In these rare cases, the Investigator must obtain documented approval from the Sponsor or Sponsor designee to allow the subject to continue in the study.

Subjects who discontinue study treatment will not be replaced.

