8.2.7 Final Visit (Day 28) or Early Termination Visit

Every attempt should be made to complete all visits during the defined window periods. Subjects who do not complete all required study visits and withdraw from the study before Day 28 final visit, will be asked to complete the Early Termination Visit.

- The subject or parent or guardian may apply the IP at home (not applicable for an Early Termination Visit).

The following assessments will be performed by the Investigator or designee:

- Physical examination.
- Record and review concomitant medication details.
- Record of vital signs.
- Body weight and height.
- Urine pregnancy test for female subjects ≥ 11 years old, or female patients < 11 years old who have started menstruating.
- vIGA-AD scale.
- EASI.
- POEM.
- ItchMan questionnaire.
- Review IP compliance
- Record and review AE details.
- Review study diary entries.
- Collect used and unused IP containers, study cleanser and moisturizer.

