9.5.1 Time Period and Frequency for Collecting AE and SAE Information

All SAEs will be collected from the signing of the informed consent form (ICF) until the final visit (or Early Termination Visit), at the timepoints specified in the SoA (Table 1.1).

All AEs will be collected from the signing of the ICF until the final visit (or Early Termination Visit), at the timepoints specified in the SoA (Table 1.1).

All SAEs will be recorded and reported to the Sponsor or designee within 24 hours, as indicated in [Appendix 3](#). The Investigator or designee will submit any updated SAE data to the Sponsor within 24 hours of it being available.

Investigators or designees are not obligated to actively seek AE or SAE after conclusion of the study participation. However, if the Investigator or designee learns of any SAE, including a death, at any time after a subject has been discharged from the study, and he/she considers the event to be reasonably related to the study treatment or study participation, the Investigator or designee must promptly notify the Sponsor.

The method of recording, evaluating, and assessing causality of AEs and SAEs and the procedures for completing and transmitting SAE reports are provided in [Appendix 3](#).

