10.4.3 Missing Data

Data from subjects who withdraw from the study, including AEs and any follow-up, will be included in the analyses of all outcomes.

Missing data will not be imputed.

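### The protocol does not consistently separate stopping B244 from leaving the study, and does not state which visits follow an individual or cohort dosing stop

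*Protocol*

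**What the plan says.** - **Section 4.6, individual rule.** It opens with "Dosing for any individual subject will be stopped if". The SAE bullet beneath it mentions dosing only. The non-serious AE bullet depends on an event that "warrants discontinuation from the study for that" subject's wellbeing.
- **Section 4.6, cohort rule.** It opens with "Dosing for a cohort will be stopped if" and uses the same study-exit phrase for non-serious events. It gives no instruction on visits.
- **Section 6.8.** A child who needs rescue beyond 7 days, or systemic therapy, is to be discontinued from the study. Section 4.6 stops dosing when worsening dermatitis needs other medication, and points to 6.8.
- **Section 7.1 (stopping treatment).** On what happens next it says only: "Subjects who discontinue study treatment will not be replaced".
- **Section 7.2 (leaving the study).** Children who withdraw because of an AE are sent to a follow-up visit. Table 1.1 has no such visit; its last columns are Day 28 and Early Termination.
- **Section 8.2.7.** Subjects who "withdraw from the study before Day 28 final visit, will be asked to complete the Early Termination Visit".
- **Section 9.5.1.** "All AEs will be collected from the signing of the ICF until the final visit (or Early Termination Visit").
- **Sections 10.3, 10.4.2 and 10.4.3.** Every enrolled child with at least one dose is in the ITT population, which carries all safety analyses. Data from withdrawn subjects are included, and "Missing data will not be imputed".

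**The concern.** Stopping a treatment and leaving a study are different events. If a site treats the first as the second, scheduled observation ends because of the outcome under study. Safety and tolerability is the primary objective, and TEAE incidence is its first endpoint.

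A child who exits early stays in the ITT denominator after a shorter period of questioning and examination. Summaries at later visits then under-represent children who stopped B244 because they tolerated it badly. About 6 centers are planned, and they could handle the same event differently. Section 10.4.2 tabulates TEAEs leading to discontinuation of study treatment, so the analysis relies on a distinction that the conduct sections blur.

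**Working it through.** The protocol gives no figure to reproduce on this point beyond 3 cohorts × 12 = 36 subjects, which agrees. The check is mainly a comparison of texts.

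**Step 1. What each rule ends**

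| Rule | Wording ends |
|---|---|
| 4.6 individual, possibly related SAE | dosing |
| 4.6 individual, significant non-serious AE | dosing by its heading, study by its criterion |
| 4.6 individual, worsening dermatitis | dosing |
| 6.8, rescue over 7 days or systemic therapy | study |
| 4.6 cohort, possibly related SAE | dosing |
| 4.6 cohort, more than 2 subjects with a qualifying non-serious AE | dosing for the cohort; study exit for the subjects with the event |

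Stopping is tied to leaving in the non-serious AE criterion and in 6.8. Elsewhere the text mentions dosing alone.

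**Step 2. Which visits follow**

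- *Child leaves the study:* Early Termination Visit (8.2.7), and AE collection closes there (9.5.1). If the reason is an AE, 7.2 adds a visit that the schedule does not contain.
- *Child stops B244 and has not withdrawn:* 7.1 is silent. Section 8.0 requires adherence to the schedule, so remaining on Table 1.1 is a fair inference, but no sentence says so.
- *Child without an event in a halted cohort:* also unstated, with the same inference available.

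**Step 3. What the exit reading would cost**

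Post-baseline visits fall on Days 7, 14, 21 and 28. Days lost = 28 − stop day; visits lost = scheduled visits after the stop day.

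| Stop day | Visits lost (of 4) | Days lost (of 28) |
|---|---|---|
| 7 | 3 | 21 (21/28 = 75%) |
| 14 | 2 | 14 (50%) |
| 21 | 1 | 7 (25%) |

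One Early Termination Visit replaces part of this. It includes vital signs, physical examination, the efficacy scales and AE recording, but it does not restore the remaining days.

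**Step 4. How many children a cohort halt could touch**

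Up to 12 of 36 (33%), fewer if some have already finished. One possibly related SAE is enough. With an assumed per-child risk p (not in the protocol), the chance of that trigger in a cohort of 12 is 1 − (1 − p)^12: 11.4% at p = 1%, 21.5% at 2% and 46.0% at 5%. Section 2.2 reports no SAEs with B244 so far, so the low end may be the more relevant.

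**The case against.** A reader might infer that the protocol as a whole treats stopping B244 as leaving the study. The documents do not support that. Sections 7.1 and 7.2 are separate, 8.0 speaks of continuing or discontinuing study treatment, and the SAE bullets in 4.6 stop dosing only. No sentence ends visits merely because dosing has stopped.

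A reader might also infer that children in a halted cohort have no visits at all. That goes too far. Table 1.1 is set by study day, and a child who has not withdrawn can be read as staying on it, with AE collection running to the final visit.

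Other points on this side also stand:

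- Known events are not abandoned. The investigator remains responsible for serious, related or discontinuation-causing AEs (9.5), SAEs are followed to resolution or stabilization (9.5.3), skin irritation likewise (9.3.5), and unscheduled visits are available (8.2.3).
- Section 10.4.3 brings withdrawn subjects' data, including any follow-up, into the analyses.
- Selection on tolerance applies to individual stops. A cohort halt also stops children who had no event, so it does not select on each child's own tolerance.
- Handling unequal time at risk is ordinarily a matter for the statistical analysis plan, which is not shown.

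The gap itself remains. An analysis plan can adjust for unequal time but cannot recover visits that did not take place, and follow-up of a known event does not detect a new one.

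**Conclusion.** The point holds as an inconsistency that should be corrected. Sections 4.6 and 6.8 mix stopping treatment with leaving the study, 7.1 states no visit schedule after a stop, and 7.2 cites a visit that Table 1.1 lacks. Following the exit-worded rules as written shortens scheduled safety observation because of the outcome. For the SAE and cohort rules the text is silent rather than wrong.

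The loss ranges from 1 visit and 7 days (Day 21 stop) to 3 visits and 21 days (Day 7 stop), before allowing for the exit visit. These figures assume that the site reads the stop as an exit and that visits fall on their nominal days. No count of missed events is claimed: that would need an event rate and an off-treatment hazard, neither of which the protocol gives.

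**What to change.** Reconcile 4.6, 6.8, 7.1, 7.2, 8.2.7, 9.5.1 and Table 1.1, so that each rule says whether it ends treatment, participation or both. The stopping criteria and their thresholds stay as they are; how the wording of 4.6 and 6.8 is brought into line is for the sponsor. Then state that:

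1. a child who stops B244, individually or because the cohort is halted, and has not withdrawn consent stays on the existing Table 1.1 assessments and AE collection through Day 28, without the investigational product steps;
2. the Early Termination Visit is for those who leave the study;
3. the follow-up visit in 7.2 refers to a visit that exists in Table 1.1;
4. values recorded after the last application are flagged as off-treatment.

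The cost is amendment wording and one flag in the eCRF. No new visit is created. The downside is that some families are asked to return after treatment has stopped; they remain free to withdraw.
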